5.1. Research methods

Data will be extracted using online questionnaires. These questionnaires will be built in Microsoft Forms, the results from which are sorted in Microsoft Sharepoint. In this way, results are automatically added when a form is completed, and assigned to the correct row using the participant's study ID, assigned to them once they are recruited. Video footage of the physical assessments will be filmed with a camera, before the footage is locally stored on the V drive, and also a backup of the footage is made in Sharepoint.

Once the study is complete, an archive of the study data will be created, and stored for 10 years using the facilities afforded to us by the Erasmus MC.

5.2. Standard clinical care versus extra for research

N/A

5.3. Burden and risks

Aside from mild nausea which may occasionally occur during a virtual reality experience, we do not foresee any risks or burdens incurred with participation. Any nausea typically subsides quickly once the head mounted display is removed.

5.4. Medical device(s) / In vitro diagnostic tests

N/A

6. Incidental findings

6.1. Chance of incidental findings

Is there a chance of incidental findings?

Yes

No

6.2. Procedures

If yes, describe who will be notified and how the subjects and other parties will be notified in case of incidental findings from the study that may be in the interest for the participant's health.

7. Statistical analysis

Describe how data will be analyzed

7.1 Main study parameters/endpoints

The accuracy with which the predetermined sequence of steps involved in an ECMO circuit check is performed by the participant. This is defined as number of mistakes made, and amount of prompts/assistance required from the expert perfusionist present at the assessment. Additionally, time to

accurately perform the predetermined endpoints/steps in the protocol of performing a circuit check as defined in Appendix 3.

7.2 Secondary study parameters/endpoints

USE questionnaire (Appendix 2) to include participant ratings on the perceived usefulness, satisfaction, ease of use, and level of immersion of the VR-ECMO sim. Additional data include participants views on the advantages and disadvantages of virtual reality training in the context of ECMO.

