to provide prompts when a student is unsure how to perform a certain step. After completion of the assessment, the VR group will be asked to fill out an objective questionnaire (Appendix 2) based on the standardised USE questionnaire [2] to assess baseline characteristics such as prior experience/training and the usefulness, satisfaction, and ease of use of the VR training modality. Participants from the control group will be given the option to also perform the VR training, and subsequently fill a USE questionnaire about their experience with VR.

Expert Arm

Expert participants will not be randomised, and will all perform the VR-ECMO sim before completing the USE questionnaire. Their data will be used for the face and content validity portion of this study.

Randomisation

Participants in the novice arm will be randomly assigned to either interventional or control group, using <https://www.randomizer.org/> as stated above to generate a group allocation for the participant according to their study ID number.

Blinding

Participants will not be blinded as the differences in the differing nature of the intervention versus control group do not allow for this. Selected study personnel, including those physically facilitating both groups during the intervention phase will not be blinded, as again the study design does not allow for this. Study personnel who facilitate the physical assessment for the novice arm, perform data collection & analysis, including the expert assessor for the video recording, will be blinded.

Burden and risks

We do not foresee any risks or burdens incurred with participation, aside from mild nausea which may occasionally occur during a virtual reality experience. This typically subsides quickly once the head mounted display is removed.

Recruitment and consent

Our study will recruit from two populations for the expert and novice arms of this study. For the former, 10 experts who are experienced perfusionists/intensivists with more than 6 years of experience with ECMO will be included. For the novice arm, the population will include intensive care nurses & cardiothoracic surgery nurses who work at one of the academic hospitals in the Netherlands, with no prior experience with ECMO. We calculated a required sample size of 44 novice participants (22 per group) in order to likely achieve statistically significant results.

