In a related study on the VR-Extracorporeal Simulator (entitled “Virtual Reality Simulation as a Training Tool for Perfusionists in Extra Corporeal Circulation; Establishing Face and Content Validity” currently under peer-review), we showed that experts and novices alike found the simulator to be useful & realistic, and therefore valid for face and content validity. Due to the demonstration of feasibility in a closely related simulator, we aim to demonstrate face and content validity alongside concurrent validity in a single study for the VR-ECMO sim. We hypothesise that VR will enable participants to better learn and retain information through interactive engagement with a virtual reality ECMO simulator versus conventional training.

2. Objective(s)

In this study, the goal is to assess the face, content, and concurrent validity of the VR-ECMO sim by comparing the questionnaire ratings of novices and experts after completing the VR-ECMO sim, and comparing the novice intervention group who completed the VR-ECMO sim versus the control arm (video training) in terms of how well they are able to perform an ECMO circuit check, as rated by an expert.

3. Study type

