4.5 Sample size calculation

We calculated a required sample size of 32 novice participants (16 per group) in order to likely achieve statistically significant results in the Novice RCT arm. This is based on an alpha of 0.05, beta of 85, and a mean difference of 1. The expert group requires 10 participants in order to reasonably assess the face & content validity.

5. Methods

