Appendix 2 - User Experience USE Questionnaire

		1. Fully disagree	2. Disagree	3. Neutral	4. Agree	5. Fully agree	N/A
	Usefulness						
1	I learned a lot from this simulation about how to perform an ECMO circuit check						
2	The training helped me being more confident in managing ECMO patients						
3	The training helped me remember the steps an ECMO circuit check						
4	After the training, I have enough knowledge to take the lead in an ECMO circuit check						
	Satisfaction						
6	I enjoyed participating in this ECMO simulation						
7	I was satisfied with the quality of this simulation						
8	I would recommend using this simulation to other colleagues						
9	I would prefer VR training additionally to conventional training (shadowing an expert)						
10	I would prefer VR training instead of conventional training (shadowing an expert)						
	Ease of use						

11	The software is easy to use						
12	I learned to use it quickly						
13	The interaction with the software felt intuitive						
14	I can use the software without written instructions						
Immersiveness							
15	I was not distracted during the training						
16	The simulator was realistic						
17	I felt like I was in a real ICU box						
18	I was interested in the progress of the events within the simulation						
19	I felt actively involved in the patient scenario of the training						

Please list and rank, in order of importance from most (1) to least (3), the advantages and disadvantages of training to use an ECMO machine in VR:

Advantages:

- 1.
- 2.
- 3.

Disadvantages:

- 1.

2.

3.

Do you have any additional suggestions or recommendations for enhancing or adding new features to the simulation?

Thank you for participating

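### No printed rated item in Appendix 2 directly asks the experts whether the simulated ECMO circuit check contains the right steps, shown correctly, although content validity is a stated aim

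*Combined protocol and SAP*

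**What the plan says.** Section 1 gives the aim: "we aim to demonstrate face and content validity alongside concurrent validity in a single study for the VR-ECMO sim". Section 2 says that validity will be assessed in part "by comparing the questionnaire ratings of novices and experts after completing the VR-ECMO sim". The Summary (Expert Arm) says that the experts "will all perform the VR-ECMO sim before completing the USE questionnaire", and adds: "Their data will be used for the face and content validity portion of this study". Section 4.5 gives the number: "The expert group requires 10 participants in order to reasonably assess the face & content validity".

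Section 7.2 names the four areas the questionnaire covers: "USE questionnaire (Appendix 2) to include participant ratings on the perceived usefulness, satisfaction, ease of use, and level of immersion of the VR-ECMO sim". Section 7.4 gives general two-group tests and no criterion for content validity.

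The Summary and section 1 also show how the team has reasoned before. In the related simulator study, experts and novices found the tool useful and realistic, and validity for both face and content was concluded from that.

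**The concern.** Face validity asks whether the simulator looks and feels credible. Content validity, in its ordinary sense, asks whether it covers the right material correctly. Here that means whether the circuit check in the simulator has the steps it should have, shown as they should be. Experienced perfusionists and intensivists can judge this. Novices without ECMO experience cannot.

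If the experts' form never puts the question, the content-validity half of the expert arm rests on an inference from other ratings. The gap lies in what is collected, so no threshold, test or summary score chosen later can close it. The study could then report content validity for a simulator in which a step is absent or wrong, with nothing in the rated data to reveal it.

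**Working it through.** The documents give no figure to reproduce on this point. The check is a reading of every form against the content-validity aim, followed by the precision that 10 experts would give on the proposed rows.

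**1. What each form asks**

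| Form and block | Rated items | What is rated | Asks if steps are present, correct or missing? |
|---|---|---|---|
| Appendix 2, Usefulness (1–4) | 4 | Own learning, confidence, recall, readiness to lead a check | No |
| Appendix 2, Satisfaction (6–10) | 5 | Enjoyment, overall quality, recommendation, preference relative to conventional training | No |
| Appendix 2, Ease of use (11–14) | 4 | Handling of the software | No |
| Appendix 2, Immersiveness (15–19) | 5 | Distraction, realism, sense of place, interest, involvement | No |
| Appendix 1 | – | Respondent's background | No |
| Appendix 3 (13 steps) | – | Novices' performance in the physical assessment; the plan does not give it to experts to rate | Not asked of experts |

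Rated items printed in Appendix 2: 4 + 5 + 4 + 5 = 18. Items that directly rate step content: 0 of 18.

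**2. The nearest items**

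- Item 16, "The simulator was realistic", is one overall rating placed under Immersiveness. It names no step.
- Item 7 rates satisfaction with the quality of the simulation as a whole.
- Items 1 and 3 ask what the respondent learned or remembered, not whether what was taught is right or complete.

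**3. Would these ratings respond to a content error?**

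- Suppose the simulator omitted one circuit-check step. An expert could still truthfully give the top score for enjoyment, intuitive handling, involvement and realism, and no rated item would prompt a report of the omission.
- Suppose the content were perfect. An expert with more than 6 years of ECMO experience could fairly disagree with items 1 to 3, having had little to learn.

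The ratings can therefore be high with faulty content and low with sound content.

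**4. Does the novice–expert comparison help?** Prior experience with ECMO equipment is a novice exclusion criterion (section 4.4). Agreement or disagreement between novices and experts on these 18 items does not show whether the steps are right.

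**5. Precision of a per-step rating with 10 experts.** The exact (Clopper–Pearson) 95% interval for x of 10 has a lower limit L at which P(X ≥ x) = 0.025 and an upper limit U at which P(X ≤ x) = 0.025.

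- x = 10: L = 0.025^(1/10) = 0.692 and U = 1, so 69% to 100%.
- x = 9: 10·L^9·(1 − L) + L^10 = 0.025 gives L = 0.555 (check: 0.0222 + 0.0028 = 0.0250). 1 − U^10 = 0.025 gives U = 0.975^(1/10) = 0.997. The interval is 56% to 100%.

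These intervals describe what the proposed rows could show. They do not measure the size of the gap.

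**The case against.** The strongest reply is that the plan has its own rule: ratings of usefulness and realism count as evidence for face and content validity, as in the related study. On that rule the usefulness items and item 16 are the structured content-validity data, and no section assigns items to face or to content. This stands in part. A reader might infer that the trial collects no data at all bearing on content validity, and the documents do not support that. They support a narrower statement: no printed rated item addresses step content directly, and the plan's route to content validity is an indirect inference that step 3 of the working shows to be weak.

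Two further points limit the claim.

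- **Free text.** Respondents rank three advantages and three disadvantages of VR training and may suggest improvements or new features. An expert could mention a wrong or missing step there. But the prompts do not ask for it, and silence cannot be read as endorsement.
- **Item 5.** The numbering runs from 4 to 6. An item may have been deleted, or lost when the text was read from PDF. Its position between Usefulness and Satisfaction, and the absence of a content domain in section 7.2, make a content item unlikely but do not exclude it. A single global item would in any case give no step-by-step rating.

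A reader might also infer that the 13-step scoring sheet used in the randomised comparison has never been endorsed by experts. The documents do not say who wrote or reviewed Appendix 3, and silence is not evidence that nobody did. They also do not list the simulator's steps or state that they are the same 13. The randomised comparison does not depend on the expert questionnaire.

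**Conclusion.** The point holds in its limited form. Content validity is an explicit aim and one of two stated uses of the expert data, yet 0 of the 18 printed rated items directly asks experts whether the steps are present and correct. The planned inference from global usefulness and realism ratings cannot reveal a missing or wrong step, and later analysis cannot recover an answer that was never requested.

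The conclusion rests on three assumptions: Appendix 2 as printed is the form experts will receive; the absent item 5 is not a content item; and content validity is meant in the ordinary sense of right material correctly shown. It does not extend to the randomised comparison or to the standing of its scoring sheet.

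This should be changed before experts are enrolled. It does not prevent the trial from running.

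**What to change.** Add one page to the expert form listing the 13 Appendix 3 steps. For each step ask:

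- 'shown correctly in the simulator' (1–5, with a 'not shown' option);
- 'needed in a circuit check' (1–5).

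Close with one open question: 'any step missing or wrong?'. The 'not shown' option and the open question are needed because the documents do not say that the simulator's steps match Appendix 3.

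In section 7.4, state that for each step the number and share of the 10 experts scoring 4 or 5 will be reported with an exact 95% confidence interval. Base the content-validity statement mainly on these rows, described as descriptive because n = 10, with the usefulness and realism ratings as supporting data.

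If the page is not added, limit the conclusion to face validity and perceived usefulness.

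Cost: 13 × 2 = 26 ratings plus one open question, assumed to take a few extra minutes for each of 10 experts already attending, and one form page. No extra staff are needed.

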7.3 Other study parameters

Data will be collected on the participants age, gender, experience with ECMO, and experience with VR usage.

7.4 Analysis

Please describe how the analysis will be done for the outcome parameters.

R version 4.2.2 will be used for analysis. Continuous data will be assessed for normal distribution using a Q-Q plot and Shapiro Wilk test. The data will be described as median (IQR) or means (SD) and compared using either an unpaired t-test or the Mann-Whitney U test (whichever is appropriate according to the distribution) will be used to determine significance. Categorical variables will be reported as numbers (%) and compared using a chi-squared test or fishers exact test (whichever is appropriate according to the distribution). All baseline characteristics and outcome data will be compared using abovementioned tests. In case of confounding variables, we will correct for these using Analysis of Covariance (ANCOVA). A P-value of <.05 will be considered statistically significant.

8. Ethical considerations

8 Regulation statement

The study will be conducted according to the principles of the Declaration of Helsinki (64th WMA General Assembly, Fortaleza, Brazil, October 2013), Gedragscode Gezondheidsonderzoek 2022 and in accordance with ISO 27799:2016(en) standards, regulations and Acts.

8.1 Informed consent

Will the subjects be asked for informed consent?

Yes (*Upload Participant Information Letter and Informed Consent*)

No, consent already given in previous study (*Upload Participant Information Letter and Informed Consent previous study*)

No, this research will be performed under the exception consent (*Upload form Care for data Template, in Dutch: Formulier uitzondering toestemming*)

Other (e.g. partly, indirectly) *Please describe the situation.*

8.2 Recruitment and informed consent procedures

If yes, please give a description of the recruitment and informed consent procedures. How and by whom (investigator, supervising doctor, other person) participants will be informed about the

study and asked for their consent, how much time will they be given to consider the decision. The patient information letter with informed consent form should be attached as a separate document.

The recruitment process will be performed by a combination of poster advertisements featuring a QR code where participants can sign up. These posters will be hung in areas where eligible staff are likely to gather e.g. break rooms. On the sign-up page, the participants will be asked to enter name and contact details, and then will be presented with the participant information form as attached as an appendix to this application. Once they have read this sheet, and agreed to it in the form by selecting 'I wish to participate' from multiple choice question, they will be taken to a further webpage where the option will be given to select a date on which to participate

8.3 Exception consent

N/A

9. Handling and storage of data / images / sound recordings / photos / film recordings

Data / images / sound recordings / photos / film recordings

Please describe which data / images / sound recordings / photos / film recordings is/are used, are they obtained for regular healthcare purposes or in the context a research project, or a combination.

In line with Erasmus MC guidelines, all video footage recordings will be kept 10 years after it is collected. The videos of the assessments will be stored on Microsoft Sharepoint, with filenames labelled only with the participants' study ID. Only the PI, research coordinator, and the expert who will assess the videos will be granted access to them.

9.1 Privacy protection

Describe how subject's privacy is protected. Describe how, when and by whom data is coded (unique code without initials or date of birth) and how the key table is safeguarded, mention the General Data Protection Regulation.

The handling of data will comply with the EU General Data Protection Regulation and the Dutch Act on Implementation of the General Data Protection Regulation (in Dutch: Algemene Verordening Gegevensbescherming en Uitvoeringswet Algemene Verordening Gegevensbescherming. A key table is produced and stored on Microsoft Sharepoint with only the PI and Research Coordinator who will be granted access to it. The rest of the data is stored in a separate table containing no identifiable personal information. The latter database includes all of the data from the questionnaires and the results from the assessments. The final data include the videos of the assessment, which stored on sharepoint, labelled only with the participants study ID. Only the PI, research coordinator, and the expert who will assess the videos will be granted access to them.

9.2 Handling and storage of data

Describe how data is handled and stored (i.e., which data management system/data capture system), anonymous / pseudonymized / coded / identifiable, who has access to the coded source data, how long data will be kept, which steps are taken to ensure data security, what happens with the data after the research has been completed.

Each pseudonymised participant data set will be assigned a study number known by the investigator. Using these coded study numbers, offline data will be stored using SPSS. Data will be stored on an Erasmus MC local network drive with automatic overnight back-up. Stored data regarding anonymous data sets and personnel included in this study can only be accessed by the investigators, the Erasmus MC ethics committee, Erasmus MC auditors and Erasmus MC monitors and any person or

agency required by law like the “Inspectie voor de Gezondheidszorg”. All data will be treated according to the “Wet Bescherming Persoonsgegevens” and the Erasmus MC privacy regulations. Any information from this study, if published in scientific journals or presented at scientific meetings, will not reveal participant identity. Data will be stored for a minimum of 10 years according to Erasmus MC guidelines, and a maximum of 15 years after ending the study. Collected data will be secured against unauthorised access and will be stored and secured by the department of Cardiothoracic Surgery.

9.3 Handling and storage of images / sound recordings / photos / film recordings

Describe how images / sound recordings / photos / film recordings are handled and stored, how the subject's privacy is protected, anonymous / pseudonymized / coded / identifiable, what happens with images after the research has been completed.

As above, the videos of the assessment will be stored on Microsoft Sharepoint, labelled only with the participants study ID. Only the PI, research coordinator, and the expert who will assess the videos will be granted access to them. After the completion of the study, in line with Erasmus MC guidelines, all video footage recordings will be kept 10 years after they are collected, and will be destroyed after 10 years.

9.4 Approval of access to data / images / sound recordings / photos / film recordings

Describe how the access is approved. Is access granted by the Data Board, Department, Principal investigator of the collection or other?

Access is determined by the primary research team (PI + Project Coordinator), and only members of the research team and any authorized audit bodies may access the video recordings.

10. Handling and storage of human material

